5.4 Treatment

In the interferon arm patients will commence treatment four weeks after nucleos(t)ide analogue withdrawal with pegylated interferon α 2a 180 mcg s.c once weekly for 16 weeks. The first injection will be administered in the clinic supervised by an experienced research nurse or clinical nurse specialist.

5.5 Follow-up

In the control arm visits 3-6 will be used to monitor safety. In the Interferon arm visits 4 - 8 will be used to monitor and manage the side effects of interferon therapy.

Biological samples will be taken according to the relevant visit schedule in Section 5.3.

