2.4 Secondary Endpoints

Efficacy endpoints

- The proportion of patients who achieve HBsAg loss who also have undetectable HBV DNA
- The proportion of patients in each group who become inactive HBV carriers; ie achieve a sustained virological response (HBV DNA < 2000 IU/mI & normal ALT values) at 3 years after randomisation
- Magnitude of reduction in quantitative HBsAg levels at 1, 6, 12, 24 & 36 months after randomisation
- Magnitude of changes in antiviral T cells response at 1, 5, 6, 12, 24 & 36 months after randomisation
- Magnitude of changes in NK cells response at 1, 5, 6, 12, 24 & 36 months after randomisation

Safety endpoints

• Proportion of patients in each group with exaggerated hepatitis flares

- Proportion of patients resuming nucleos(t)ide analogue therapy
- Adherence to pegylated interferon therapy

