5.3 Visit Schedules Control Arm

Control A	,,,,											1	1
Visit number	1	2	3	4	5	6	7	8	9	10	11	12	13
Week	-4	0	4	8	12	16	24	32	52	78	104	130	156
Control Group	Screening ²	Baseline	Post week 4	Post week 8	Post week 12	Post week 16	Post week 24	Post month 8	Post month 12	Post Month 18	Post month 24	Post month 30	Post month 36
Consent	Х												
Demographic data	х												
Inclusion / Exclusion		Х											
Randomisation		Х											
Medical history	Х												
Vital signs	х	Х	Х	Х	Х	х	Х	х	Х	Х	Х	х	Х
Physical examination	х								Х		Х		х
Liver biopsy ¹	х												
USS/Fibroscan	х												
HBV Genotyping			Х										
qHBsAg	х												
HBsAg		Х	Х				Х		Х		Х		Х
HBV DNA	х	Х	Х	Х	Х	Х	Х	Х	Х	Х	Х	х	Х
LFTs	Х	Х	Х	Х	Х	Х	Х	Х	Х	Х	Х	х	х
Thyroid function	х												
Electrolytes & creatinine	х												
Prothrombin time	х	Х	Х	Х	Х	Х	Х	Х	Х	Х	Х	Х	Х
FBC	Х		Х				Х	Х	Х	Х	Х	х	х
PBMC collection (for immunology assays)		Х	Х				Х		Х		Х		х
Plasma/serum storage (for virology)		Х	х				Х		Х		Х		х
Adverse events		Х	Х	Х	Х	х	Х	Х	Х	Х	Х	х	х
Concomitant medications	х	Х	Х	Х	х	х	Х	х	Х	Х	Х	х	Х
Pregnancy test		Х											

Liver biopsy to be performed between screening and baseline in a sub-set of ~20 patients, 2. Baseline to occurs 4 – 12 weeks after initial screening

PROTOCOL Version 2.0 12th Aug 2016

Sponsor Imperial College

Interferon arm

Visit number	1	2	3	4	5	6	7	8	9	10	11	12	13	14	15	16
Week	-4	0	4	6	8	12	16	20	24	32	42	52	78	104	130	156
Interferon Group	Screening ²	Baseline	Gap week 4	IFN week 2	IFN week 4	IFN week 8	IFN week 12	IFN week 16	Post IFN week 4	Post IFN week 12	Post IFN week 22	Post randomisation month 12	Post randomisation Month 18	Post randomisation month 24	Post randomisation month 30	Post randomisation month 36
Consent	х															
Demographic data	х															
Inclusion / Exclusion		х														
Randomisation		х														
Medical history	х															
Vital signs	х	х	х	х	х	х	х	х	х	х	х	Х	Х	Х	Х	Х
Physical examination	х											Х		Х		Х
Liver biopsy ¹	х															
Ultrasound/Fibroscan	Х															
HBV Genotyping			х													
qHBsAg	х															
HBsAg		х	Х						х			Х		Х		Х
HBV DNA	х	х	х	х	х	х	х	х	х	х	х	Х	Х	Х	Х	Х
LFTs	х	х	х	х	х	х	х	х	х	х	х	х	Х	Х	Х	Х
Thyroid function	х				х			х		х						
Electrolytes & creatinine	Х		Х			Х		Х		Х		Х				
Prothrombin time	х	х	х	х	х	х	х	х	х	х	х	Х	Х	Х	Х	Х
FBC	х		Х	Х	Х	Х	Х	Х	Х		Х	х		Х		Х
PBMC collection (for immunology assays)		Х	х					Х	Х			х		Х		Х

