5.6 Laboratory Evaluations

(i) Haematology

Full blood counts and prothrombin times will be measured using standard methods in the routine haematology department at each participating site.

(ii) Biochemistry

Liver function tests (bilirubin, albumin, ALT, alkaline phosphatase), thyroid function tests (TSH & T4), glucose, electrolytes and creatinine will be measured using standard methods in the routine haematology department at each participating site.

(iii) HBV DNA

HBV DNA will be measured quantitatively using real-time PCR based assays in the routine virology departments at each participating site. Results will be reported back on the eCRF.

(iv) HBV genotype

Plasma from an EDTA specimen taken at week 4 will be collected and processed at each participating site and stored at -80°C until transported to Virology at UCLH. Genotyping will be performed by sequence analysis of the HBV DNA.

(v) HBsAg quantification

A quantitative HBsAg measure will be performed at each local hospital on a screening visit blood sample. The result will be used for stratification in the randomisation system.

HBsAg concentrations will be performed using the Abbott Architect qHBsAg system in [name] laboratory. Serum samples will be collected in the virology department at each participating site and stored at -80°C until transported, frozen, in batches to Virology at UCLH.

(vi) Liver Biopsy

In patients who consent to have a liver biopsy as part of the study the procedure will be performed by a trained hepatologist or radiologist and two passes will be made with the biopsy needle to obtain 2 liver specimens of 1.5 - 2 cm in length. One of these will be placed in to 10% formaldehyde and sent to the histology laboratory for paraffin embedding and sectioning. The first 2 sections will be used for standard H&E and pico-sirius red staining to assess necroinflammatory and fibrosis scores. Two sections will be used for immunohistochemistry staining for HBsAg and HBV core antigens. Two sections will be sent to [name] laboratory for measurement of cccDNA.

The second liver specimen will be collected in sterile PBS and sent by courier to [name] laboratory.

(vii) ELISPOT

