6.4 Hepatitis Flare

A hepatitis flare is defined as an ALT greater than twice the upper limit of normal (ALT> 2 X ULN). If a patient reaches this level at any visit they will be asked to return for an unscheduled visit at which further blood tests will be taken. If the patient continues to meet the criteria for a flare they will continue to be seen at unscheduled visits until the flare has resolved (at which point they will return to the routine visit schedule) or if the flare worsens and meets the definition of an exaggerated flare they will recommence nucleos(t)ide analogues as described below.

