8.2 Data Analysis

(i) Primary Endpoint Analysis

This analysis will be performed primarily on an intention to treat (ITT) basis. The ITT population will be all subjects who have been randomized. Secondarily, a per protocol analysis will be performed. The per protocol population will be those confirmed to be eligible who have not resumed nucleos(t)ide analogues for patient/ physician preference and those, in the interferon arm, who have completed at least 8 weeks of interferon therapy. Rates of HBsAg loss will be compared between the two groups using logistic regression adjusting for the stratification factors HBsAg titre and centre. Results will be presented as odds ratios and their 95% confidence intervals.

(ii) Secondary outcomes

Secondary outcomes to be compared between the two groups will include the primary outcome assessed at one year and at two years from baseline. Kaplan-Meier plots will be produced to show the persistence of HBsAg. The plots will be supported by formal secondary analyses using Cox proportional hazards model methods

Achievement of the inactive carrier state (defined above) will be analysed using the same procedures as the primary outcome. A statistical analysis plan will be developed and approved by the Trial Steering committee prior to any regular analysis for reports to the Data Monitoring Committee. This plan will include details of the statistical methods to be used to analyse the outcomes, and describe the methods to undertake sensitivity analyses for handling missing data. The plan will contain conform with the Clinical Trials Unit standard operating procedures

(iii) Predictors of HBsAg Loss

Predictive factors for HBsAg loss will be explored using univariate and multivariate logistic regression analysis. Separate models will be fitted for the following variables: gender, age, duration of antiviral therapy, viral genotype, viral load pre-treatment, HBsAg titre, centre, peak ALT value post withdrawal, peak viral load post withdrawal, hepatic cccDNA, number of infected hepatocytes and ELISPOT counts. Odds ratios and their 95% confidence intervals produced from each of the models will be presented. Following this, a multivariate logistic regression analysis will be performed will include the variables that were statistically significant in the univariate analysis plus a variable for treatment group.

(iv) Safety analysis

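### First-year liver tests are scheduled 10 times in the interferon arm and 7 times in control, with an unexplained 20-week control gap, so flare and resumption proportions are open to unequal detection

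*Protocol*

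**What the plan says.** The two visit tables in protocol section 5.3 give these weeks:

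- Control: "Week -4 0 4 8 12 16 24 32 52 78 104 130 156"
- Interferon: "Week -4 0 4 6 8 12 16 20 24 32 42 52 78 104 130 156"

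In both tables liver function tests, prothrombin time and HBV DNA are marked at every visit. Section 5.6 confirms that the liver panel carries the two analytes that matter here: "Liver function tests (bilirubin, albumin, ALT, alkaline phosphatase".

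Section 5.5 explains some of the difference. For control, "In the control arm visits 3-6 will be used to monitor safety"; for interferon, visits 4 to 8 (weeks 6 to 20) serve to manage side effects of the drug. The week 42 visit is interferon visit 11, labelled "Post IFN week 22", and lies outside that range.

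Section 2.4 lists as a safety endpoint "Proportion of patients in each group with exaggerated hepatitis flares", and also the proportion who resume nucleos(t)ides. Section 6.5(i) makes the exaggerated-flare criteria the criteria for resumption. Extra visits depend on a result already in hand; section 6.4 states: "If a patient reaches this level at any visit they will be asked to return for an unscheduled visit". Section 5.3 also allows discretionary visits for flares or other safety reasons. Section 8.2(iii) lists "peak ALT value post withdrawal, peak viral load post withdrawal" among the candidate predictors of HBsAg loss.

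**The concern.** In the main design both arms stop nucleos(t)ides at week 0, so both are at risk of a flare from the same day. A transient rise in ALT, bilirubin or INR is recorded only if blood is taken while it lasts. The arm tested more often will then show more events even when the true rates are equal.

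The mandatory unscheduled visits in section 6.4 do not correct this, because they start only after a raised ALT has been seen. Adverse event reporting is not a second source either. Section 7.3 excludes liver test and HBV DNA abnormalities, and section 7.4(iii) keeps exaggerated flares out of the adverse reaction and event record and leaves them to the case report form.

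At stake is the evidence for the second objective in section 2.2, whether interferon with treatment cessation is safe. Section 6.5(i) also plans to look for systematic differences between groups in retreatment, and unequal testing can produce such a difference by itself.

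**Working it through.** **The plan's own figures.** The protocol gives no flare duration and no detection rate, so there is none to reproduce. Its sample size of 109 per arm (40% v 20%, 90% power, two-sided 5%) does reproduce with pooled variance and no continuity correction. This point does not touch it.

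**Step 1: tests after baseline, from section 5.3.**

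- Control to week 52: weeks 4, 8, 12, 16, 24, 32, 52. That is 7 tests, with gaps 4, 4, 4, 4, 8, 8, 20 (sum 52).
- Interferon to week 52: weeks 4, 6, 8, 12, 16, 20, 24, 32, 42, 52. That is 10 tests, with gaps 4, 2, 2, 4, 4, 4, 4, 8, 10, 10 (sum 52).
- After week 52, both arms: weeks 78, 104, 130, 156.

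The longest first-year gap is 20 weeks in control (32 to 52) and 10 weeks in interferon. Interferon alone is tested at weeks 6, 20 and 42.

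**Step 2: illustrative detection probability.** Assume an abnormality of duration D weeks, onset uniform over weeks 0 to 52, and detection only at scheduled visits. An onset within a gap g is caught at the next visit if it falls in the last min(g, D) weeks of that gap. Hence

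detection = sum over gaps of min(g, D) / 52.

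| D (weeks) | Control | Interferon | Difference (points) | Of which weeks 32-52 |
|---|---|---|---|---|
| 2 | 14/52 = 26.9% | 20/52 = 38.5% | 11.5 | 2/52 = 3.8 |
| 4 | 28/52 = 53.8% | 36/52 = 69.2% | 15.4 | 4/52 = 7.7 |
| 8 | 40/52 = 76.9% | 48/52 = 92.3% | 15.4 | 8/52 = 15.4 |
| 10 | 42/52 = 80.8% | 52/52 = 100% | 19.2 | 10/52 = 19.2 |
| 12 | 44/52 = 84.6% | 52/52 = 100% | 15.4 | 8/52 = 15.4 |
| 16 | 48/52 = 92.3% | 52/52 = 100% | 7.7 | 4/52 = 7.7 |
| 20 or more | 100% | 100% | 0 | 0 |

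From 8 weeks upward the whole difference arises in weeks 32 to 52. At 4 weeks half of it does, and the other half comes from the week 20 test. For onsets within weeks 32 to 52 and D = 8, detection is 8/20 = 40% in control and 16/20 = 80% in interferon.

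**Step 3: pilot review.** Section 3.1 times it after the therapy gap and two months of interferon, about week 12. By then control has 3 tests (gaps 4, 4, 4) and interferon 4 (gaps 4, 2, 2, 4). For D of 4 weeks or more both sums are 12, so there is no difference. For D = 2 they are 6/12 and 8/12. Patients recruited early may be further on, but for D of 8 weeks or more the sums are still equal at week 32 (32 v 32).

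**Step 4: primary endpoint.** After baseline, HBsAg is marked at weeks 4, 24, 52, 104 and 156 in both tables, so sampling for HBsAg loss is the same in both arms.

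**The case against.** The strongest reply has four parts.

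**The extra visits are deliberate.** Visits for drug toxicity in one arm are normal in an open-label trial, and section 5.5 states that purpose. This stands for weeks 6 and 20. It does not cover week 42, when interferon has long ended and Table 1 describes both arms simply as in follow-up.

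**The arithmetic is not about the endpoint.** A reader might take 54% v 69% as detection rates for exaggerated flares. The documents do not support that. The exaggerated criteria in section 6.5(i) include elevation for more than 6 months, which a 20-week gap cannot hide, and a judgement of risk by investigator or patient, which need not wait for a scheduled test. A simple flare already found is followed at unscheduled visits in either arm, so later worsening would be caught. Symptoms may also bring patients in early. All of this stands. The calculation shows direction and rough scale for a transient laboratory abnormality, no more.

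**The reach is limited.** A reader might infer that the pilot 40% rule is distorted, that HBsAg loss is biased, or that peak ALT and peak HBV DNA are compared unfairly between arms. Step 3 shows little effect on the pilot. HBsAg sampling is matched; an effect through earlier retreatment would be indirect, and the documents give no way to size it. The peaks are planned only as predictors, with treatment group in the multivariate model, so the harm there is measurement error that depends on arm.

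**Counting rules belong in the statistical analysis plan.** That is often so. But the schedule is fixed in this protocol, and a sample never drawn cannot be recovered by analysis.

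**Conclusion.** The point holds in a limited form. First-year testing is 7 v 10, and nothing in the protocol explains why control goes untested between weeks 32 and 52 while interferon is tested at week 42. The between-arm proportions with exaggerated flares and with nucleos(t)ide resumption are therefore subject to differential detection, towards more events in the interferon arm.

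Under the stated assumptions the gap in detection is 11.5 to 19.2 points for abnormalities lasting 2 to 12 weeks, 7.7 points at 16 weeks, and nil from 20 weeks. It depends on durations and onset times that the protocol does not give. Onset concentrated in the first 16 weeks would remove it for durations of 4 weeks or more; onset in weeks 32 to 52 would enlarge it. Attendance for symptoms would narrow it.

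A reader might conclude that flare rates cannot be compared at all. That goes too far: the schedules match after week 52, and prolonged flares are found equally in both arms.

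**What to change.** In section 8.2(iv), state that the between-arm comparisons of exaggerated flares and of nucleos(t)ide resumption will each be reported twice:

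1. from all visits; and
2. from the visits scheduled in both arms (weeks 4, 8, 12, 16, 24, 32, 52, 78, 104, 130 and 156) plus the unscheduled visits that arise from them.

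This is analysis work only. If the unscheduled visit form does not already record what prompted the visit, it needs that item. The downside is that the common-visit count may drop flares found and retreated at weeks 6, 20 or 42 in the interferon arm, and so understate harm there. For that reason neither count should stand alone.

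Separately, the sponsor should reconcile the two schedules in section 5.3 between weeks 32 and 52, or state the purpose of the difference. Which weeks to use is for the sponsor to decide. Any added control draw would mean an extra visit for those patients.

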5.6 Laboratory Evaluations

(i) Haematology

Full blood counts and prothrombin times will be measured using standard methods in the routine haematology department at each participating site.

(ii) Biochemistry

Liver function tests (bilirubin, albumin, ALT, alkaline phosphatase), thyroid function tests (TSH & T4), glucose, electrolytes and creatinine will be measured using standard methods in the routine haematology department at each participating site.

(iii) HBV DNA

HBV DNA will be measured quantitatively using real-time PCR based assays in the routine virology departments at each participating site. Results will be reported back on the eCRF.

(iv) HBV genotype

Plasma from an EDTA specimen taken at week 4 will be collected and processed at each participating site and stored at -80°C until transported to Virology at UCLH. Genotyping will be performed by sequence analysis of the HBV DNA.

(v) HBsAg quantification

A quantitative HBsAg measure will be performed at each local hospital on a screening visit blood sample. The result will be used for stratification in the randomisation system.

HBsAg concentrations will be performed using the Abbott Architect qHBsAg system in [name] laboratory. Serum samples will be collected in the virology department at each participating site and stored at -80°C until transported, frozen, in batches to Virology at UCLH.

(vi) Liver Biopsy

In patients who consent to have a liver biopsy as part of the study the procedure will be performed by a trained hepatologist or radiologist and two passes will be made with the biopsy needle to obtain 2 liver specimens of 1.5 - 2 cm in length. One of these will be placed in to 10% formaldehyde and sent to the histology laboratory for paraffin embedding and sectioning. The first 2 sections will be used for standard H&E and pico-sirius red staining to assess necroinflammatory and fibrosis scores. Two sections will be used for immunohistochemistry staining for HBsAg and HBV core antigens. Two sections will be sent to [name] laboratory for measurement of cccDNA.

The second liver specimen will be collected in sterile PBS and sent by courier to [name] laboratory.

(vii) ELISPOT

30-40 ml of peripheral blood will be collected into heparinised tubes. Samples will be transported by courier to [name] laboratory at the Institute of Hepatology. Peripheral blood mononuclear cells (PBMC) will be extracted using standard laboratory techniques and then frozen in liquid nitrogen until used for analysis in batches. Immunology samples will also be collected at unscheduled visits if the patient experiences a hepatitis flare.

(viii) NK Cells

PBMCs from [name] laboratory will be transferred to the [name] laboratory for analysis of NK cell numbers and activation status using fluorescence activated cell sorting techniques (FACS) after staining with monoclonal antibodies.

(ix) Sample storage

10 ml serum samples will be taken at several timepoints (denoted on the visit schedule), processed at each participating site and stored at -80°C until transferred to Imperial College. These will be stored in the Imperial Biobank and used in future research to explore virological, metabolic or immunological determinants of clinical response.

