1.2.2 Virology studies

HBsAg loss is associated with clearance of HBV-infected hepatocytes and elimination of cccDNA. Earlier studies suggest that the change in HBsAg concentrations in serum reflect the changes in cccDNA concentration in hepatocytes and therefore may represent an ideal biomarker for identifying patients who are moving towards HBsAg loss.

Samples will be taken at various timepoints to track the dynamics of HBsAg concentration changes and to enable an analysis of the predictive value of this biomarker. HBsAg concentrations will be performed using the Abbott Architect qHBsAg system in [name] laboratory.

		Sponsor
NUC-B	PROTOCOL Version 2.0 12 th Aug 2016	Imperial College

There are 7 different genotypes and a number of variants in the pre-C/C and S open reading frames of the hepatitis B virus. Viral genotypes have been associated with variation in the natural history of infection and with the response to treatment. At baseline all patients will have undetectable virus in their serum but samples taken 4 weeks after withdrawal should have sufficient circulating virus to allow genotype and sequencing of the virus. Genotyping with be performed in [name] laboratory.

In patients undergoing liver biopsy prior to baseline a sample will be used to measure the cccDNA level quantitatively using an in-house real-time PCR assay in [name] laboratory

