3 STUDY DESIGN

3.1 Pilot Phase

A pilot phase will be conducted at the beginning of the trial. This will consist of 50 patients recruited across 4 sites. Milestones within the pilot are based on numbers of patients recruited as well as safety aspects/numbers of exaggerated flares as shown in the flow diagram below. The pilot phase will be conducted according to the same protocol as the main trial and the pilot phase patients will count towards the overall trial sample size. Exaggerated flares are defined in Section 6.4 (i).

The milestones for the pilot phase are as follows:

- If the pilot phase fails to recruit 40 patients in 4 months then NIHR-EME will discontinue the study.
- If more than 40% of patients in either arm of the trial experience exaggerated flares by the end of the pilot phase then that arm will be discontinued. If this occurs in the interferon arm then the interferon arm will be modified to a control and combined interferon treatment protocol in which pegylated interferon is added to the nucleos(t)ide analogue for 16 weeks prior to cessation of therapy rather than leaving a gap between nucleos(t)ide analogues withdrawal and pegylated interferon treatment (and compared to the control arm still) see Figure 2. If this occurs in the control arm then the control arm will be switched to the interferon and combined interferon treatment protocol (and compared against the standard interferon arm) see Figure 3.
- If more than 60% of patients in the pilot experience exaggerated flares the trial will be discontinued.
- If more than 40% of patients in both arms experience exaggerated flare by the end of the pilot phase then the trial will be terminated if the DMEC and TSC recommend so.

A safety assessment will be made by the TSC and DMEC when all pilot patients will have completed initial screening, therapy gap and two months of interferon therapy. The trial will be assessed against the above milestones and a decision on the continuation of the trial made.

NUC-B	PROTOCOL Version 2.0 12 th Aug 2016	Sponsor Imperial College	
		impenal College	

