5 PROCEDURES AND MEASUREMENTS

The trial will be open label meaning that both patients and their medical staff will know to which arm of the trial they are randomised. All patients in the trial will discontinue nucleos(t)ide analogues at baseline with the exception of the interferon arm in the alternative protocol (see Figures 2 and 3).

Occurrence of flares which require recommencement of nucleos(t)ide analogues will be an important measure of safety and efficacy in this trial and will therefore not be counted as a withdrawal from the study. Based on the previous studies of treatment cessation it is reasonable to expect up to 45% of patients to require retreatment.

A. Control arm

Patients randomised to the control arm will discontinue their nucleos(t)ide analogue treatment at baseline. They will be followed up until 3 years after randomisation.

B. Interferon arm

Patients randomised to the Interferon arm will discontinue their nucleos(t)ide analogue treatment at randomisation. No treatment will be given for 4 weeks and then they will commence pegylated interferon 180 mcg s.c. o.w α 2a and will continue taking weekly interferon for a total of 16 weeks. They will subsequently discontinue all antiviral medications. They will be followed up until 3 years after randomisation.

Although pegylated interferon has a long list of side effects which may be both unpleasant for the patients and potentially harmful, poor adherence to treatment is not anticipated. All the centres in this study are experienced in the use of pegylated interferon for the treatment of both HBV and HCV infection and invariably achieve adherence rates over 95%.

Control and combined interferon treatment Protocol – see Figure 2

By the end of the pilot phase, if more than 40% of patients in the interferon arm experience exaggerated flares then the arm will be modified to a control and combined interferon treatment protocol in which pegylated interferon is added to the nucleos(t)ide analogue for 16 weeks from randomisation and prior to cessation of therapy rather than leaving a gap between nucleos(t)ide analogues withdrawal and pegylated interferon treatment (and compared to the control arm still). They will subsequently discontinue all antiviral medications after the 16 weeks. They will be followed up until 3 years after randomisation.

Interferon and combined interferon treatment Protocol – see Figure 3

NUC-B PROTOCOL Version 2.0 12 th Aug 2016	Sponsor Imperial College

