Plasma/serum storage (for virology)		х	х					Х	Х			х		Х		Х
Adverse events		х	Х	х	Х	х	Х	Х	Х	Х	х	Х	Х	Х	Х	Х
Concomitant medications	х	Х	х	Х	Х	Х	Х	Х	Х	Х	Х	х	х	Х	Х	Х
Pregnancy test		Х	Х													

Liver biopsy to be performed between screening and baseline in a sub-set of ~20 patients, 2. Baseline to occurs 4 – 12 weeks after initial screening

PROTOCOL Version 2.0 12th Aug 2016

Sponsor Imperial College

Alternative Protocol Interferon Arm

Visit number	1	2	3	4	5	6	7	8	9	10	11	12	13	14	15	16
Week	-4	0	2	4	8	12	16	20	24	28	40	52	78	104	130	156
Interferon Group	Screening ²	Baseline	IFN week 2	IFN week 4	IFN week 8	IFN week 12	IFN week 16	Post IFN week 4	Post IFN week 8	Post IFN week 12	Post IFN week 24	Post randomisation month 12	Post randomisation Month 18	Post randomisation month 24	Post randomisation month 30	Post randomisation month 36
Consent	Х															
Demographic data	х															
Inclusion / Exclusion		х														
Randomisation		х														
Medical history	х															
Vital signs	х	х	х	х	х	х	х	х	х	х	х	Х	Х	Х	Х	Х
Physical examination	х											Х		Х		Х
Liver biopsy ¹	х															
Ultrasound/Fibroscan	х															
HBV Genotyping								х								
qHBsAg	х															
HBsAg		х		х				х				Х		Х		Х
HBV DNA	х	х	х	х	х	х	х	х	х	х	х	Х	Х	Х	Х	Х
LFTs	х	х	х	х	х	х	х	х	х	х	х	Х	Х	Х	Х	Х
Thyroid function	х			Х			х				х					
Electrolytes & creatinine	Х				Х		Х			Х		х				
Prothrombin time	х	х	х	Х	х	х	х	Х	х	х	х	Х	Х	Х	Х	Х
FBC	Х		Х	Х	Х	Х	Х	Х			х	х		Х		Х
PBMC collection (for immunology assays)		х						Х		х		х		Х		Х
Plasma/serum storage (for virology)		Х						Х		Х		х		Х		Х
Adverse events		х	Х	х	х	х	х	Х	х	х	х	Х	Х	Х	Х	Х
Concomitant medications	Х	Х	Х	Х	Х	х	Х	Х	х	Х	х	х	х	Х	Х	Х
Pregnancy test		х														

1. Liver biopsy to be performed between screening and baseline in a sub-set of ~20 patients, 2. Baseline to occurs 4 – 12 weeks after initial screening

Additional visits may be made during interferon therapy to support or instruct patients but these will not be considered as study visits and will not be recorded in the study CRF.

Additional visits may be made at the discretion of the investigator for safety monitoring if hepatitis flares occur or for other safety reasons. These will be recorded in the unscheduled visit form.

Visit windows/tole	erance.

Arm	Visit	Tolerance
Interferon Arm	2	2 weeks – 3 months
(including	3-12	+/- 3 days
alternative	13-16	+/- 10 days
interferon arms)		
Withdrawal	2	2 weeks – 3 months

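### HBV genotype rests on one specimen taken 4 weeks after nucleos(t)ide withdrawal with no repeat, so it would be missing according to early viral rebound (minor; cheap to improve)

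*Protocol*

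**What the plan says.** - **Specimen.** Protocol section 5.6(iv): "Plasma from an EDTA specimen taken at week 4 will be collected and processed at each participating site". No arm is named. Genotype is read by sequencing the HBV DNA in that plasma.
- **Why that time.** Section 1.2.2 gives the starting point, "At baseline all patients will have undetectable virus in their serum", and then the expectation that "samples taken 4 weeks after withdrawal should have sufficient circulating virus to allow genotype and sequencing of the virus". It gives no expected proportion and no minimum viral load for sequencing.
- **Schedules.** In section 5.3 the row "HBV Genotyping" carries one mark in each table: week 4 for the control arm, week 4 for the standard interferon arm, and week 20 (visit 8) for the alternative, combined-interferon arm.
- **Which text governs.** Section 5.5: "Biological samples will be taken according to the relevant visit schedule in Section 5.3".
- **Combined arm.** Section 5 says that "pegylated interferon is added to the nucleos(t)ide analogue for 16 weeks from randomisation and prior to cessation of therapy". Under section 3.1 this regimen comes into use only on a pilot trigger: "If more than 40% of patients in either arm of the trial experience exaggerated flares by the end of the pilot phase".
- **Use of genotype.** Section 8.2(iii) lists it among the candidate predictors of HBsAg loss: "gender, age, duration of antiviral therapy, viral genotype, viral load pre-treatment, HBsAg titre, centre, peak ALT value post withdrawal", and others. It is neither a stratification factor (5.2) nor a term in the primary model (8.2(i)).
- **Other material.** HBV DNA is measured at every visit in all three schedules. Plasma or serum for virology is stored at several later visits, but section 5.6(ix) assigns the stored serum to future research and does not mention genotyping.

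**The concern.** Sequencing needs circulating virus, and the protocol starts every patient from undetectable virus. A single attempt at a fixed time therefore yields a genotype only in patients who have rebounded enough by then. Whether genotype is known becomes a consequence of what happened after the drug was stopped, and the speed of rebound may itself be related to HBsAg loss.

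Section 1.2.2 says that genotype has been associated with natural history and treatment response, and Secondary Objective 4 is to find virological and immunological predictors of HBsAg loss. If genotype is significant in its univariate model, it enters the multivariable model in 8.2(iii). A fit restricted to patients with complete data would then drop the ungenotyped patients for every other predictor too. An analysis plan can choose a missing-data method, but it cannot recover a genotype that was never sequenced, so the sampling rule belongs in the protocol.

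A second, separate matter is that section 5.6(iv) and the alternative schedule give different weeks for the same specimen.

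**Working it through.** **1. Weeks from nucleos(t)ide withdrawal to the scheduled specimen** (genotyping mark in 5.3 minus week of withdrawal)

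| Arm | Withdrawal | Genotyping mark | Difference |
|---|---|---|---|
| Control | week 0 | week 4 | 4 - 0 = 4 weeks |
| Standard interferon | week 0 | week 4 | 4 - 0 = 4 weeks |
| Combined interferon | week 16 | week 20 | 20 - 16 = 4 weeks |

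The schedules are consistent with each other and with section 1.2.2. Read literally for the combined arm, 5.6(iv) would place the specimen at week 4, which is 16 - 4 = 12 weeks before withdrawal.

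**2. Repeat or fallback.** Each schedule has one genotyping mark. Sections 1.2.2, 5.3 and 5.6 state no repeat, no viral-load trigger and no alternative specimen.

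**3. Size, under an assumed range.** The protocol states no figure to reproduce. Let f be the share of patients with too little virus at the scheduled visit; the documents do not give f. Patients genotyped = 240 x (1 - f). The planned loss rates in 8.1 are 20% and 40%, an average of 30%, so complete data would hold about 0.30 x 240 = 72 events. If loss is unrelated to rebound, events among genotyped patients = 0.30 x 240 x (1 - f).

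| f (assumed) | Genotyped | Events |
|---|---|---|
| 0% | 240 | 72 |
| 10% | 216 | 65 |
| 20% | 192 | 58 |
| 30% | 168 | 50 |
| 40% | 144 | 43 |

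**4. Selection, illustrated.** If loss is 30% overall and r0 among the ungenotyped, loss among the genotyped is r1 = (0.30 - f x r0) / (1 - f). With f = 20%:

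- r0 = 10%: r1 = (0.30 - 0.02) / 0.80 = 35%
- r0 = 30%: r1 = (0.30 - 0.06) / 0.80 = 30%
- r0 = 50%: r1 = (0.30 - 0.10) / 0.80 = 25%

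The genotyped subset can thus have a higher or a lower loss rate than the whole trial, and the documents do not fix the direction. For the genotype odds ratio itself to be distorted, rebound would also have to differ by genotype; the protocol gives no data on that.

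**5. Samples available for a fallback** (5.3, storage row, after the scheduled genotyping visit)

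- Control: weeks 24, 52, 104, 156
- Standard interferon: weeks 20, 24, 52, 104, 156
- Combined interferon: weeks 28, 52, 104, 156

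**The case against.** **The protocol expects enough virus at 4 weeks.** Nothing in it contradicts section 1.2.2, and the true share of failures could be close to zero. This stands. The 10% to 40% range is an assumption, and the link between early rebound and HBsAg loss is an inference.

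**The consequence is small.** Genotype is one of twelve variables listed for exploration, no power claim attaches to that analysis, and 8.2(ii) leaves missing-data methods to the statistical analysis plan. This also stands and sets the severity. A reader might infer that the main treatment comparison is compromised. It is not, because genotype plays no part in it.

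**The combined-arm specimen is correctly timed.** From 5.6(iv) alone a reader might infer that it is drawn under suppression and that hardly any of those patients could be sequenced. The documents do not support this. That arm's own schedule puts genotyping at week 20, 4 weeks after the nucleos(t)ide stops, and 5.5 makes the schedule govern. What is left is an unreconciled week in 5.6(iv), for an arm that may never be opened.

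**Repeat sequencing is not forbidden and could sit in a laboratory manual.** This is partly right. But the stored serum is assigned to future research, so using it for a trial variable needs a stated permission, and a repeat left to discretion could be applied unevenly across sites or arms.

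**Conclusion.** The point holds as a minor one. In all arms genotype depends on one specimen 4 weeks after withdrawal, with no second attempt, so it would be missing in patients who have not rebounded enough by then. Only the exploratory predictor analysis in 8.2(iii) is affected. The size is unknown: under the assumed 10% to 40% failure range, 216 to 144 of 240 patients would be genotyped and about 65 to 43 of 72 expected events retained, with selection on top if rebound is related to loss. The conclusion rests on sequencing needing circulating virus, which section 1.2.2 implies, and on the single marks in the schedules being all that is done.

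The difference between week 4 in 5.6(iv) and week 20 in the alternative schedule is a wording conflict, not a mistimed specimen.

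**What to change.** In section 5.6(iv), replace the fixed week by a rule:

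- Genotype the first post-withdrawal sample with enough HBV DNA to sequence, and state the threshold that the laboratory uses.
- Start at the scheduled genotyping visit for the arm: week 4 in the control and standard interferon arms, week 20 in the combined-interferon arm. This also brings 5.6(iv) into line with the alternative schedule.
- If that sample is too low, use the plasma or serum for virology already stored at later visits, chosen from the HBV DNA results already measured at each visit.
- In section 5.6(ix), allow stored samples to be used for this purpose.

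The cost is a wording change, a few repeat sequencing runs and some stored volume that would otherwise go to future research. No visit, randomisation or treatment changes.

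The rule will not recover every patient. In the control arm no virology sample is stored between weeks 4 and 24, and section 5 expects up to 45% of patients to need retreatment. Someone who rebounds and restarts within that gap may still have no sample that can be sequenced. The number left ungenotyped should therefore be reported by arm.
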